## 7. Statistical Methods

### 7.1 General Principles

All data processing, summarization and analyses will be performed using Covance's SAS Environment / Version 9.4 (or later) of the SAS® statistical software package.

The following principles will be applied to all TFLs unless otherwise stated:

Principle	Value
Significant tests	Results will be considered statistically significant at one sided alpha of 0.025, and considered to indicate promising trend at one sided alpha of 0.2.

**CONFIDENTIAL**

Document Date: 29 Nov 2021

Page 15 of 34  
ST-AD-008 version 05

## Statistical Analysis Plan

Sponsor Name: Golden Biotechnology Corporation  
 Sponsor Protocol ID: GH Covid-2-001

Covance Study ID: 000000203201

Principle	Value
Treatment group labels and order	Antroquinonol 100 mg BID Placebo
Tables	Data in summary tables presented by treatment group, assessment and visit (where applicable).
Listings	All data collected presented by treatment group, country, site, Patient, assessment and visit (where applicable), unless otherwise specified.
Descriptive summary statistics for continuous variables	Number of patients/observations (n), mean, standard deviation (SD), median, minimum (Min) and maximum (Max).
Descriptive summary statistics for categorical variables	Frequency counts and percentages [n (%)]
Denominator and for percentages	Number of patients in the analysis population, unless stated otherwise in table shell(s).
Precision for percentages	1 decimal place
Include "Missing" as category	Yes, when the number missing is greater than zero for at least one treatment group.
Display to one more decimal place than collected value	For efficacy and safety: Mean Mean Difference Median
Display to two more decimal places than collected value	For efficacy and safety: Standard Error Standard Deviation Confidence Interval
Display to three significant figures	For PK: Mean Standard Deviation Geometric Mean Median Min Max
Limit of precision for displays	4 decimal places
Date Format	DDMMYYYY

## 7.2 Patient Disposition and Data Sets Analyzed

Patient disposition will be listed and summarized by treatment group and overall for the all enrolled population and will include the number and percentage of patients that fall into the categories below:

- screened (overall);
- screen failed, including a breakdown of the primary reasons for screen failure;
- eligible but not randomized;
- randomized;
- randomized but not treated;
- treated;

**CONFIDENTIAL**

Document Date: 29 Nov 2021

Page 16 of 34  
 ST-AD-008 version 05

## Statistical Analysis Plan

Sponsor Name: Golden Biotechnology Corporation

Sponsor Protocol ID: GH Covid-2-001

Covance Study ID: 000000203201

- included in each study population (ITT set, mITT set, PPS, SS, PKS);
- completed/discontinued from the study treatment, including a breakdown of the primary reasons for discontinuation;
- completed/discontinued from the study, including a breakdown of the primary reasons for discontinuation.

Summary of patient disposition by country and site will be provided for each treatment group and overall for the ITT set.

### 7.3 Protocol Deviations

All protocol deviations will be listed for the ITT set.

All important protocol deviations leading to exclusion from the PPS (see Section 5.4.1) will be listed and summarized by treatment group and overall for the ITT set.

### 7.4 Baseline Disease Characteristics

Baseline disease characteristics will be listed and summarized by treatment group and overall for the ITT set. Standard descriptive statistics will be presented for the continuous variables of:

- oxygen saturation (SpO2) (%);
- WHO COVID clinical improvement ordinal scale.

The total counts and percentages of patients will be presented for the categorical variables of:

- patient setting;
- chest imaging result (normal, abnormal NCS, abnormal CS);
- SARS-CoV-2 test result (negative, positive);
- WHO COVID clinical improvement ordinal scale (at or below each score);
- COVID-19 symptoms;
- COVID-19 symptoms – maximum severity;
- patients with diarrhea.

### 7.5 Demographics and Other Baseline Characteristics

Demographic and other baseline characteristics will be listed and summarized by treatment group and overall for the ITT set. Standard descriptive statistics will be presented for the continuous variables of:

- age (years);
- weight (kg);
- height (cm);
- body mass index (BMI, kg/m^2) [calculated as (weight/height) where weight is in kg and height is in m].

**CONFIDENTIAL**

Document Date: 29 Nov 2021

Page 17 of 34

ST-AD-008 version 05

## Statistical Analysis Plan

Sponsor Name: Golden Biotechnology Corporation  
Sponsor Protocol ID: GH Covid-2-001

Covance Study ID: 000000203201

The total counts and percentages of patients will be presented for the categorical variables of:

- age ( $\leq$  65 years,  $>$  65 years);
- sex;
- race;
- ethnicity;
- remdesivir use or other authorized treatments for COVID-19.

Other baseline measurements, such as vital signs and ECG, will be summarized with the post-baseline measurements.

### 7.5.1 Medical History

Medical history will be coded using Medical Dictionary for Regulatory Activities (MedDRA) [Version 23.0 dated 19 Apr 2020 or a later version if updated during the study (exclusively meant for COVID-19)]. All medical history will be listed, and the number and percentage of patients with any medical history will be summarized for the ITT set by system organ class (SOC) and preferred term (PT) for each treatment group and overall.

### 7.5.2 Prior and Concomitant Medications

Medications received prior to or concomitantly with study treatment will be coded using WHODrug Dictionary [Version Global B3 March 2020 (or a later version if updated during the study)].

Prior medications and concomitant medications are defined as follows:

Prior medications are those with a stop date prior to the first dose date of study treatment.

Concomitant medications are those with a start date on or after the first dose date of study treatment, or those with a start date before the first dose date of study treatment and a stop date on or after the first dose date of study treatment or ongoing end of study.

If a medication cannot be classified as "prior" or "concomitant" due to missing/incomplete dates, it will be classified as concomitant.

Prior medications and concomitant medications will be listed together and summarized separately for the ITT set.

The number and percentage of patients using each medication will be displayed together with the number and percentage of patients using at least one medication within each therapeutic class (ATC-Level 2) and generic term.

## Statistical Analysis Plan

Sponsor Name: Golden Biotechnology Corporation  
Sponsor Protocol ID: GH Covid-2-001

Covance Study ID: 000000203201

### 7.6 Efficacy

Efficacy analyses will be conducted on ITT set, mITT set and PPS, separately, unless otherwise specified. The ITT set will be the primary analysis population for efficacy and the mITT set and PPS will be the supportive analysis populations for efficacy analysis. If it turns out that ITT and mITT populations are identical, then only ITT results will be presented.

#### 7.6.1 Primary Efficacy Analysis

The proportion of patients from each treatment group who are alive and free of respiratory failure on Day 14 will be summarized and compared using logistic regression, with treatment, remdesivir or other authorized treatments for COVID-19 use at baseline (yes vs no) and age at baseline ( $> 65$  years vs  $\leq 65$  years) as covariates. The p-value for treatment effect will be provided based on the Wald test. P-value based on Fisher's exact test will also be provided. Odds ratio along with its 95% confidence interval will be provided based on the exact method. In addition, the risk difference for the treatment effect and 95% confidence interval will be calculated based on the proportion of patients alive and respiratory failure free in the control group and the estimates of odds ratio, along with its 95% confidence interval.

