Patients will undergo assessment during hospitalization or could be discharged after start of study treatment any time after Day 2 if judged to be ready for discharge. If discharged, patients will then be requested to take study treatment at home (as prescribed) up to Day 14. End of Treatment assessments at Day 14 (+2 days) (at home or site visit) will be performed. A Day 5 (+/- 1 day) visit (at home or site visit) will be performed if the patient is discharged prior to Day 5. If the patient is discharged after completion of treatment and before the follow-up visit, he/she will be followed up on Day 28 (± 2 days) for study assessments (a telephone or telemedicine visit). Post discharge, assessments will be done by telephone or telemedicine, except for Day 5, Day 14, and Early Termination (ET) of Study Treatment. If the discharge, ET, or Early Withdrawal visit falls within the window of a scheduled Day visit, the assessments for the visits can be combined as one visit. On days of laboratory assessments, discharged patients will have a home visit. On days of no laboratory assessments, discharged patients will complete their assessments via telephone, telemedicine, or other means of remote communication. Additionally, patients will receive a diary to capture all doses after a discharge.

Number of patients:

A total of 174 patients are planned to be randomized into the study:

- 20 patients in the sentinel cohort (10 patients in each treatment group)
- 154 patients in the expansion cohort (77 patients in each treatment group).

This enrollment level ensures 80% power to demonstrate proof of concept efficacy with one-sided alpha of 0.2.

The sample size is based on the following assumptions:

- The randomized allocation ratio is 1:1 between the antroquinonol group and the placebo group
- The proportion of patients alive and free of respiratory failure is approximately 78% on placebo vs 89% on antroquinonol
- The following nonbinding rules will be considered by the DMC for futility, and the DMC will not make any recommendations to stop for early efficacy:
 - Interim analysis 1 (sentinel cohort): An odds ratio of 3.5 on the primary endpoint in favor of placebo.

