5.3. Method of treatment assignment

All patients will either receive antroquinonol or placebo after randomizing in a 1:1 ratio using an Interactive Web Response System (IWRS). Before the study is initiated, the log in information and directions for the IWRS will be provided to each site.

Randomization will be stratified by remdesivir or other authorized treatments for COVID-19 use at baseline and age at baseline (≤ 65 years vs > 65 years).

Patients confirmed eligible at screening will be assigned a patient identifier prior to the administration of study treatment. The patient identifier will consist of the country number, site number, and patient number. The country number will comprise the first 2 digits, the site number will comprise the next 3 digits, and the patient number will comprise the final 3 digits eg, 01002003 is Country 1, Site 2, Patient 3.

Study treatment will be dispensed at the Day 1 visit (see Schedule of Assessments, [Appendix 5](#)).

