8.4.1. Primary efficacy outcome measures

The proportion of patients from each treatment group who are alive and free of respiratory failure on Day 14 will be compared using logistic regression. The p-value will be based on the Wald test. The primary model will be stratified by remdesivir or other authorized treatments for COVID-19 use at baseline and by age at baseline (> 65 years vs ≤ 65 years).

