#### 7.6.2 Secondary Efficacy Analysis

##### 7.6.2.1 Clinical Improvement Score as Measured by WHO COVID-19 Clinical Improvement Ordinal Scale

Clinical improvement measured as a score on the WHO COVID-19 Clinical Improvement Ordinal Scale will be analyzed using an ordinal logistic regression on Days 7, 14, and 28, with study treatment, clinical improvement score at baseline (as numerical variable), age at baseline ( $> 65$  years vs  $\leq 65$  years), and remdesivir or other authorized treatments for COVID-19 use at baseline (yes vs no) as covariates. The p-value for treatment effect will be provided based on the Wald test.

In addition, descriptive statistics will be provided for average score by treatment group, and the proportion of patients at or below each score, at each visit.

Time to 2-point improvement from baseline in WHO COVID-19 Clinical Improvement score, time to score of 2 or lower, and time to score of 0, will also be analyzed. The hazard ratio and its 95% confidence interval for these time-to-event endpoints will be estimated by Cox proportional hazard model, with treatment, remdesivir or other authorized treatments for COVID-19 use at baseline (yes vs no) and age at baseline ( $> 65$  years vs  $\leq 65$  years) as covariates. The analysis will be carried out using two different censoring rules: 1) Patients will be censored at the time they are provided any authorized treatment for COVID-19 not prescribed at baseline, or on Day 28 if they have not yet recovered or have died by Day 28; 2) Patients will only be censored on Day 28 if they have not yet recovered or have died by Day 28. The p-value for comparison between treatment groups will be obtained based on the Cox proportional hazards model described above. Median time to 2-point improvement, time to score of 2 or lower, and time to score of 0 will be estimated by Kaplan-Meier (KM) method, and the KM curve will be provided.

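### The primary logistic model omits baseline WHO score (3 vs 4), a prognostic value already collected; adding it is cheap and gains a little precision

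*SAP*

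**What the plan says.** SAP 7.6.1: the Day 14 proportions alive and free of respiratory failure are "compared using logistic regression, with treatment, remdesivir or other authorized treatments for COVID-19 use at baseline (yes vs no) and age at baseline", age being split at 65. Protocol 8.4.1 names the same two factors: "The primary model will be stratified by remdesivir or other authorized treatments for COVID-19 use at baseline and by age at baseline". They are the randomization strata in Protocol 5.3: "Randomization will be stratified by remdesivir or other authorized treatments for COVID-19 use at baseline and age at baseline".

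Baseline WHO score appears elsewhere. Protocol 4.1 admits patients at score 3 or 4. Protocol Appendix 5 schedules the scale at screening and on Day 1. SAP 7.4 tabulates it by arm. The ordinal regression in SAP 7.6.2.1, run on Days 7, 14 and 28, adjusts for "clinical improvement score at baseline (as numerical variable").

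The score is not a stratum, not a covariate for the primary endpoint and not a subgroup factor in SAP 7.6.3. No sensitivity analysis of the primary endpoint adds it.

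**The concern.** Primary failure is death or a need for non-invasive ventilation, high-flow oxygen, invasive ventilation or ECMO. On the scale in Protocol Appendix 7 that is essentially score 5 or above. A patient entering at score 4 is one step from failure, and one entering at score 3 is two steps away. The omitted variable is therefore the baseline value of the scale that the outcome cuts, and it is a natural candidate for the strongest baseline predictor. The SAP adjusts for it when the same scale is analysed as an ordinal outcome and gives no reason for leaving it out when the scale is in effect dichotomized.

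At stake are a little power and protection against chance imbalance. Randomization is not stratified on the score, so the arms can differ on it. If they do, and no adjusted analysis is prespecified, any later adjustment of the go/no-go result will be post hoc and less credible.

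**Working it through.** **Inputs from the documents.** "A total of 174 patients are planned to be randomized into the study" (87 per arm, 1:1). "The proportion of patients alive and free of respiratory failure is approximately 78% on placebo vs 89% on antroquinonol". One-sided alpha 0.2, with 0.025 as the second level (Protocol 8.3). Dropout 2%, and nonbinding futility at odds ratios of 3.5 and 1.2 favoring placebo (Protocol 8.1).

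**1. The plan's own figures.** The protocol claims: "This enrollment level ensures 80% power to demonstrate proof of concept efficacy with one-sided alpha of 0.2".
- A fixed design with 87 per arm has 87.0% power.
- Simulating the final Wald test with 2% dropout, and applying both futility rules as if they were followed, gives 79.7%. This reproduces the stated 80%.
- SE of the log odds ratio = √{[1/(0.78×0.22) + 1/(0.89×0.11)]/87} = √{(5.828 + 10.215)/87} = 0.4294. Then exp(−0.8416 × 0.4294) = 0.697, the final boundary in Protocol 8.1.

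**2. Power with and without the WHO term.** The documents give no prognostic strength and no score mix, so these are assumptions: failure odds ratio (OR) for score 4 vs 3, share at score 4, and age OR per 10 years (age mean 57, SD 14, range 18–80). Each setting has 6,000 simulated trials with 170 evaluable patients, allocation balanced on the two strata, marginal success rates of 78% and 89%, and no futility stops. Each cell shows the present model → the present model plus score 3 vs 4.

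| WHO OR | Share at 4 | Age OR | Power at 0.2 | Power at 0.025 |
|---|---|---|---|---|
| 2 | 50% | 1.0 | 87.5 → 88.1 | 49.0 → 49.5 |
| 3 | 50% | 1.5 | 88.2 → 88.5 | 50.0 → 51.3 |
| 5 | 50% | 1.5 | 87.2 → 89.0 | 49.5 → 52.3 |
| 5 | 50% | 2.0 | 88.2 → 89.6 | 51.1 → 54.0 |
| 3 | 80% | 1.5 | 88.0 → 87.9 | 49.6 → 50.0 |
| 3 | 90% | 1.0 | 86.3 → 86.1 | 48.2 → 48.2 |

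A separate set of runs over WHO ORs of 2 to 6 and shares of 50–80% gave gains of about 0 to 1.3 points at 0.2 and 0.4 to 3.7 at 0.025. The 1.8-point gain in the third row is above that range. Rerunning that setting with twice as many trials gave 1.3, so the excess is simulation noise. With no treatment effect (OR 3, 50%, age 1.5), rejection at nominal 20% was 21.3% → 21.0%, and at nominal 2.5% it was 3.0% → 3.0%.

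**3. Chance imbalance.** The SD of the between-arm difference in the share p at score 4 is √{2p(1−p)/87}.
- p = 50%: 7.6 points; a difference of 10 points or more in about 19% of trials.
- p = 80%: 6.1 points; about 10%.
- p = 90%: 4.5 points; about 3%.

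With an assumed OR of 3, a 10-point imbalance multiplies the treatment odds ratio by about exp(0.10 × ln 3) = 1.12. On the log scale that is 0.110, or 0.110/0.4294 = 0.26 standard errors. It is also 0.110/0.361 = 30% of the distance from no effect to the 0.697 boundary.

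**4. Events per term.** Expected failures are 87×0.22 + 87×0.11 = 28.7. Three model terms now have 28.7/3 = 9.6 each; four would have 28.7/4 = 7.2.

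**5. Sparse cells.** Take overall failure of 16.5% and a WHO OR of 4. At an 80% share, failure among score-3 patients is about 5.6%, and the chance of none in about 35 such patients is 0.944^35 ≈ 13%. At a 90% share it is about 5.1%, and 0.949^17 ≈ 41%. The WHO term then has no finite estimate.

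**The case against.** The case for leaving the model alone is reasonable. Adjusting for exactly the randomization factors is a coherent prespecified choice, and the protocol and SAP agree on it. The gain at the design alpha is at most a point or two, on a fixed-design power of about 87%. A 50% share at score 4 is a favorable assumption: version 4.0 added room-air saturation below 94% as an entry criterion so as to enroll sicker patients, so most later patients may be on oxygen. A severity-adjusted Day 14 comparison already exists in the ordinal model, and baseline score is tabulated by arm, so imbalance would be visible. Under strong score-4 predominance the new term may not be estimable.

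Most of this stands, and it limits the size of the point. It does not remove it. The ordinal analysis is secondary and answers a different question from the go/no-go test. The sparse-cell risk calls for a stated fallback, not for omission. The cost is one degree of freedom and no new data.

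A reader might go further and infer that chance imbalance biases the primary odds ratio. It does not. After randomization, imbalance is random error already covered by the Wald standard error, it falls in either direction, and type I error is the same with and without the term. Adjustment removes some of that error.

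**Conclusion.** The omission is real, and correcting it is a cheap improvement of modest value. For a failure OR of 2 to 6 and 50–80% of patients at score 4, the gain is about 0 to 1.3 points of power at one-sided 0.2 and about 0.4 to 3.7 at 0.025. It is near zero at about 90% score 4 or if the score is weakly prognostic. All of these strengths and shares are assumptions. The better reason to act is that a severity-adjusted primary result would be prespecified if the arms happen to differ.

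Two stronger readings are tempting and not supported. One is that the trial is underpowered or its stated power wrong: 80% is reproduced once the futility rules are applied. The other is that age is mishandled and should enter in years. Age is already a stratum and a covariate at 65, and a continuous term adds only about 0 to 1 point at 0.2. With WHO score also in the model it would cut events per term to 28.7/5 = 5.7. If the SAP's exact method means exact conditional logistic regression, it would also make the conditional distribution nearly degenerate.

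**What to change.** Before unblinding, in SAP 7.6.1 and Protocol 8.4.1:
- Add baseline WHO score (3 vs 4, binary) to the primary logistic model, keeping both randomization factors. State how any patient randomized outside those two scores is coded.
- Use the same model for the Day 7 and Day 28 respiratory-failure-free analyses.
- Keep the present model as a prespecified sensitivity analysis, and as the fallback if either WHO-score group has no failures.
- Leave age as the 65-year factor; age in years is at most a further sensitivity analysis.
- Say explicitly whether the death and symptom models change. SAP 7.6.2.4 ties them to the primary model or method, and deaths may be too sparse for another term.

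The costs are one degree of freedom (about 7.2 expected failures per term instead of 9.6) and an odds ratio conditional on one more factor. The SAP should state the latter, because the two odds ratios are not the same quantity. In the setting with WHO OR 3, 50% at score 4 and age OR 1.5, the median log odds ratio moves from 0.872 to 0.911, that is, from 2.39 to 2.49. The risk difference in SAP 7.6.1 is derived from the odds ratio, so it would shift as well.

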8. SAMPLE SIZE AND DATA ANALYSES

8.1. Determination of sample size

The decision to include 20 patients in the sentinel cohort was chosen arbitrarily.

The sample size for the expansion group has been determined to provide evidence of proof of concept efficacy should the treatment prove effective. The primary endpoint and futility rules are based on assessments at Day 14 to enable rapid decision making, and the assessment at Day 28 will also be presented as a secondary endpoint.

The detailed assumptions are as follows, and the calculations include the patients from the sentinel cohort that were treated with the same dose used for the expansion cohort:

Alpha	0.2 (one-sided)
Power	80%
Drop-Outs assumed	2%
Endpoint	Odds of patient alive and respiratory failure free by Day 14
Effect Size	78% Placebo 89% Antroquinonol
Futility boundary shape	Manually chosen. Odds Ratio of 3.5 at interim analysis 1 in favor of placebo, and 1.2 at interim analysis 2 in favor of placebo. Equivalent to 4 patients not in respiratory failure on antroquinonol vs 7 on placebo at interim analysis 1, or 26 patients not in respiratory failure on antroquinonol vs 28 on placebo at interim analysis 2. Nonbinding
Efficacy boundary shape	None

In addition, the performance of the study under the following scenarios for the efficacy of antroquinonol were also considered:

Antroquinonol harmful	78% Placebo 67% Antroquinonol
Antroquinonol no effect	78% Placebo 78% Antroquinonol

The nonbinding decision rules of the interim analysis and stopping probabilities under:

Look #	Sample Size	Futility Stopping Boundary Odds Ratio	Cumulative Futility Stopping Probability		
			Drug harmful	No effect	Drug effective
Interim analysis 1	20	3.5	25%	17%	5%
Interim analysis 2	80	1.2	79%	44%	9%
Final	174	0.697			

The decision rules may be modified pending discussion with the DMC, but any modifications will still be considered nonbinding; therefore, no adjustment for the final alpha will be made.

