### 2.3 Sample Size

A total of 174 patients are planned to be randomized into the study:

- 20 patients in the sentinel cohort (10 patients in each treatment group)
- 154 patients in the expansion cohort (77 patients in each treatment group).

This enrollment level ensures 80% power to demonstrate proof of concept efficacy with one-sided alpha of 0.2.

The sample size is based on the following assumptions:

- The randomized allocation ratio is 1:1 between the antroquinonol group and the placebo group
- The proportion of patients alive and free of respiratory failure is approximately 78% on placebo vs 89% on antroquinonol

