### **7.6.2.4 Vital Status, Patients Alive and Free of Respiratory Failure, and COVID-19 Symptoms**

Proportion of patients with vital status of death in both groups on Days 7, 14, and 28 will be summarized compared using the same logistic regression model as the primary model.

Proportion of patients alive and free of respiratory failure on Days 7 and 28 will be summarized and compared using the same analysis as the primary endpoint.

Proportion of patients with each COVID-19 symptoms at baseline and on Days 7, 14, and 28 will be summarized and compared using logistic regression following the same method as the primary endpoint. Shift from baseline in severity table for each COVID-19 symptoms will be provided by treatment group.

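### As written, the 95% CI for the primary risk difference treats the placebo proportion as known and covers about 88% at the planned 78% versus 89%

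*SAP*

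**What the plan says.** SAP 7.6.1 (Primary Efficacy Analysis) compares the arms by logistic regression with treatment, baseline use of authorised COVID-19 treatment and age group as terms. For the test, "The p-value for treatment effect will be provided based on the Wald test". For the effect estimate, "Odds ratio along with its 95% confidence interval will be provided based on the exact method". It then adds a risk difference with a 95% CI, derived from the proportion of patients alive and "respiratory failure free in the control group and the estimates of odds ratio, along with its 95% confidence interval". That is the whole specification. There is no formula, and no variance, covariance, delta-method or bootstrap step; nothing elsewhere in the SAP or protocol supplies one.

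SAP 7.6.2.4 extends the method to the secondary timepoints: the proportion alive and free of respiratory failure "on Days 7 and 28 will be summarized and compared using the same analysis as the primary endpoint".

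The design assumption in SAP 2.3 is: "The proportion of patients alive and free of respiratory failure is approximately 78% on placebo vs 89% on antroquinonol". Protocol 8.1 also considers a harm scenario, "78% Placebo 67% Antroquinonol", and a no-effect scenario of 78% in both arms.

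**The concern.** The placebo proportion is itself an estimate from about 87 patients. If the odds-ratio limits are carried onto the risk-difference scale at that observed value, its sampling error enters only through the odds-ratio interval. There it carries the wrong weight, and its dependence on the converted baseline is ignored. The interval is still labelled 95%.

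What is at stake is the reported size and precision of the absolute effect, a natural input to planning a next study after a proof-of-concept trial. The size and direction of the error depend on the unknown true effect, so a reader cannot correct for it from the interval alone.

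**Working it through.** **Inputs.** 174 patients randomised 1:1, so 87 per arm (SAP 2.2, 2.3). Planned rates p0 = 0.78 and p1 = 0.89, so the true difference is 0.11 and the odds ratio 2.28 (SAP 2.3). Drop-out 2%, so about 85 per arm (Protocol 8.1). Exact 95% odds-ratio limits (SAP 7.6.1).

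**The plan's own figures.** The documents state no coverage beyond the nominal 95%, so the design figures were checked first.
- Power, stated as 80% at one-sided alpha 0.2: one-sided Fisher exact power is 81.4% with 85 per arm.
- Final odds-ratio boundary, stated as 0.697: SE(log OR) = √[1/(87×0.89×0.11) + 1/(87×0.78×0.22)] = 0.429, and exp(−0.842×0.429) = 0.697.

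Both agree, so the inputs are read correctly.

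**Formula on the natural reading.** For each odds-ratio limit, RD limit = expit(logit(p̂0) + log OR limit) − p̂0, with p̂0 held fixed.

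**Why it goes wrong (large-sample sketch).**
- Correct variance: p1q1/n + p0q0/n = 0.0979/87 + 0.1716/87 = 0.001125 + 0.001972 = 0.003098, so SE = 0.0557.
- Variance implied by the conversion: (p1q1)² × [1/(n·p1q1) + 1/(n·p0q0)] = p1q1/n + (p1q1/p0q0)² × p0q0/n. The placebo term is multiplied by (0.0979/0.1716)² = 0.325, giving 0.001125 + 0.000642 = 0.001767, so SE = 0.0420.
- The ratio is 0.0420/0.0557 = 0.755. A 1.96-SE interval behaves like one of 1.96×0.755 = 1.48 SE, which covers about 86%.
- With equal rates the multiplier is 1 and the two variances agree. Under harm it exceeds 1 and the interval is too wide.

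**Exact enumeration.** All 2×2 tables with 87 per arm, conditional exact odds-ratio limits converted as above, 78% on placebo:

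| True rate on antroquinonol | Coverage | Mean width | Newcombe mean width |
|---|---|---|---|
| 67% (harm) | 98.5% | 0.316 | 0.259 |
| 78% (no effect) | 96.8% | 0.267 | 0.244 |
| 80% | 95.9% | 0.255 | 0.240 |
| 82% | 95.1% | 0.243 | 0.236 |
| 83% | 94.3% | 0.236 | 0.234 |
| 84% | 93.6% | 0.229 | 0.232 |
| 85% | 93.0% | 0.221 | 0.230 |
| 87% | 90.8% | 0.206 | 0.225 |
| 89% (planned) | 88.1% | 0.189 | 0.220 |

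At 89%, Newcombe covers 95.3%. The plan's upper limit is below 0.11 in 8.4% of trials and its lower limit above 0.11 in 3.5%. The mean upper limit is 0.174, against 0.219 for Newcombe. With 85 per arm, coverage is 87.8%. The exact odds-ratio interval itself covers 96.9%, so the loss arises in the conversion.

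**Other odds-ratio intervals at the planned effect.**
- Mid-p limits give 85.0% and Wald limits 84.9% (87 per arm).
- Covariate-adjusted Wald limits give 83.6% to 85.4% under assumed covariate effects (85 and 87 per arm).
- If the exact method means exact logistic regression with both covariates, simulation (4,000 trials per scenario) gives 88.7%, 87.2% and 89.0%. The three settings are assumptions, not taken from the documents. As share over 65, share on authorised treatment and their two log odds ratios, they are (25%, 50%, −1.0, −0.3), (25%, 50%, 0, 0) and (40%, 70%, −1.5, −0.5).

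**Worked example, 77/87 versus 68/87.** Placebo odds are 68/19 = 3.579; the odds ratio is (77×19)/(10×68) = 2.15, with exact limits 0.876 and 5.538.
- Lower: 3.579×0.876 = 3.136; 3.136/4.136 = 0.758; minus 0.782 gives −0.023.
- Upper: 3.579×5.538 = 19.82; 19.82/20.82 = 0.952; minus 0.782 gives 0.170.

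Newcombe gives −0.008 to 0.214.

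**The case against.** The SAP lists inputs and does not state an algorithm. A delta-method calculation carrying both variances is not excluded, and a formula could sit in table shells that are not among these documents. This stands as a limit on certainty, and the conclusion is conditional on the natural reading for that reason. But if another formula was meant, the SAP still does not let anyone reproduce a prespecified interval for the primary endpoint.

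The shortfall is not general. Coverage is nominal or better under harm, at no effect and for small benefits, and it becomes material only as the effect approaches the design alternative. That also stands, and the 88% should not be quoted without it.

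No decision uses the interval. The SAP's criterion is "Results will be considered statistically significant at one sided alpha of 0.025", with a promising trend at one-sided 0.2; futility uses odds ratios; and Protocol 8.4.1 does not ask for a risk difference at all. On this reading the interval excludes zero exactly when the exact odds-ratio interval excludes 1, so it creates no extra claims of benefit. At the planned effect the error mainly understates the possible benefit: the lower-limit error is 3.5% against a nominal 2.5%. A reader with the counts by arm could compute a sound interval. All of this is correct and limits the severity, but it does not make the 95% label true.

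**Conclusion.** The concern holds. If the odds-ratio limits are converted at the observed placebo proportion, the interval covers 88.1% at the planned effect with 87 per arm, and 87.8% with 85 per arm. No odds-ratio interval tried restores nominal coverage there. Below-nominal coverage begins at about 83% to 84% on antroquinonol; at no effect and under harm the interval is too wide instead. The unadjusted figures rest only on the documents' rates and sample size; the covariate-adjusted ones rest on assumed covariate shares and effects. P-values, alpha, power and futility are unaffected. This is a fault in the reported precision of the absolute effect and should be fixed, but it does not threaten the trial's conclusions.

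**What to change.** Replace the risk-difference sentence in SAP 7.6.1 with wording such as: *The risk difference will be estimated by standardisation from the primary logistic model, as the mean predicted probability with all ITT patients set to antroquinonol minus the mean with all set to placebo, with a delta-method (or bootstrap) 95% CI.* A stratified Newcombe or Miettinen-Nurminen interval over the randomisation strata would also serve. Apply the same wording to Days 7 and 28. If a different formula was intended, state it and show that it carries the placebo proportion's sampling error.

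Across the simulated scenarios, standardisation with a delta-method CI covers 94.0% to 94.6% and stratified Newcombe 95.1% to 96.4%.

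The cost is one sentence and a few lines of code, with two consequences:
- At the planned effect the interval widens, from a mean of 0.189 to 0.220 with Newcombe or 0.206 to 0.215 with standardisation. At no effect or harm it narrows.
- Exact agreement with the odds-ratio interval about the null is lost. Newcombe and the unadjusted exact odds-ratio interval disagree in 7.1% of trials at the planned effect, 1.6% at no effect and 5.9% under harm. Standardisation and the adjusted exact interval disagree in 9.5% to 10.2% at the planned effect.

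The plan already carries a similar mismatch. Its Wald p-value (two-sided 0.05) and exact odds-ratio interval disagree there in 7.1% to 8.0% of trials (adjusted) or 7.1% to 10.8% (unadjusted). Disagreement with the Wald p-value is smaller for the replacements: 2.2% to 2.8% for standardisation and 1.0% to 5.0% for stratified Newcombe.
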